I have read this protocol in its entirety and I agree to all aspects.

Principal Investigator (*Printed Name*)

Signature

Date

Clinical Trial Protocol ATM-2201	Version 2.0 28-Oct-2022	Confidential Page 4/25
-------------------------------------	----------------------------	---------------------------

SYNOPSIS

Version	Version 2.0 (28-Oct-2022)	Study Device	Intradermal needle adapter
Study Number	ATM-2201		
Phase	Proof of Concept	Control Product	Not Applicable
Indication	Inflammatory Acne Lesions	Study Sites	1 site (US)
Title	Intralesional Injections of Triamcinolone for Acne Vulgaris		
Sponsor	ACOM Labs, Inc.		
Study Duration	14 days per subject	Sample Size	~20 subjects
Study Design	
This is an open-label, prospective, single-arm study. Approximately 20 subjects will be enrolled at 1 study site.
 
All subjects will receive standard-of-care intralesional injection with triamcinolone using an intradermal needle adapter at Visit 1 (Day 1). Subjects will then attend in-clinic visits at Visit 2 (24-hours post-injection), Visit 3 (48-hours post-injection), Visit 4 (72-hours post-injection), Visit 5 (Day 7), and Visit 6 (Day 14).
 
Efficacy assessments (target lesion assessments, photography) and safety assessments will be conducted by the Investigator at each study visit. Subjects will conduct lesion pain assessments at each study visit as well as satisfaction assessments at each post-treatment visit.
		
Study Objectives	The objective of this proof-of-concept study is to investigate the safety of using an intradermal needle adapter for performing intralesional injections.		
Inclusion Criteria	
 Outpatient, male or female of any race, 18 years of age or older. Female subjects of childbearing potential must have a negative UPT at Baseline. Diagnosed with facial acne vulgaris. At least one (1) identifiable inflammatory lesion that, in the opinion of the investigator, is clinically indicated for standard-of-care intralesional injection(s) of triamcinolone and for which the research participant has already agreed to have standard-of-care intralesional injection(s) of triamcinolone. Able to follow study instructions and likely to complete all required visits. In good general health as determined by medical history at the time of screening (Investigator discretion). Sign the IRB-approved ICF (including HIPAA authorization) prior to any study-related procedures being performed. 		
Exclusion Criteria	
 Female subjects who are pregnant or breast-feeding. Known hypersensitivity or previous allergic reaction to any constituent of triamcinolone injection. Active cutaneous viral infection in any treatment area at Baseline. Have concomitant skin disease or infection (other than acne) or presence of skin comorbidities in the areas of skin where study device will be used. History of poor cooperation or unreliability (Investigator discretion). Planning to move out of the area prior to study completion. Subjects who are investigational site staff members or family members of such employees. Exposure to any other investigational /device within 30 days prior to Visit 1. 		
Study Treatment	
Intradermal Needle Adapter: The intradermal needle adapter is an accessory that slips on the end of a standard 32G 0.5" needle and reduces the effective length of the needle to 1mm. The adapter is made of biocompatible 304 Stainless Steel. It is packaged in single use bags and will
		

Clinical Trial Protocol ATM-2201	Version 2.0 28-Oct-2022	Confidential Page 5/25
-------------------------------------	----------------------------	---------------------------

	
be autoclaved or prepared in the standard manner for typical stainless steel instruments used by the Investigator.
 
Triamcinolone for Injection: A commercial supply of triamcinolone for injection will be used for injection. The site will store triamcinolone as per the conditions described in the package insert. A standard 32G 0.5" needle will be fixed to a 1.0 mL luer syringe and the syringe will be loaded with an appropriate volume and concentration of triamcinolone. A total of 0.05 mL to 0.15 mL of triamcinolone 0.5% to 2.5% will be injected into each target lesion. The choice of volume and concentration will be at the discretion of the Investigator as per his clinical judgement. An intradermal needle adapter will then be installed on the needle.
 
At least one (1), and up to three (3) inflammatory target lesions will be selected for intralesional injections of triamcinolone using the intradermal needle adapter.

Blinding	Not applicable
Investigator Assessments	
 Global Severity Score (GSS): A 5-point scale assessing ranging from 0 (Clear) to 4 (Severe). Note: only Baseline assessments will be conducted. Target Lesion Erythema: A 5-point scale ranging from 0 (No Erythema) to 4 (Very Severe Erythema). Target Lesion Severity: A 5-point scale ranging from 0 (None) to 4 (Very Severe). Target Lesion Improvement: A 7-point scale ranging from 1 (Clear; 100%) to 7 (Worse). Target Lesion Videography: A video will be taken of each injected lesion starting from just prior to needle penetration and up to 10 seconds after removed of needle from lesion. Target Lesion Photography: Photographs will be taken at each study visit of each injected inflammatory lesion. At Baseline, photographs will be taken both pre- and post-injection.
Subject Assessments	
 Target Lesion Pain: Target lesion pain will be self-assessed by the subject using a Visual Analog Scale Intralesional Injection Pain: Target lesion injection pain will be self-assessed by the subject using a Visual Analog Scale. Subject Satisfaction: A 5-point scale ranging from 1 (Very satisfied) to 4 (Very dissatisfied).
Safety Endpoints	Adverse Events
Sample Size	Approximately 20 subjects will be enrolled. This is a POC study and a formal sample size justification is not provided for this study. It is the opinion of the Sponsor that a total of 20 subjects will be sufficient to achieve the objective of the study.
Statistical Methods	
For categorical parameters, the number and percentage of subjects/observations in each category will be presented. The denominator will be based on the number of subjects/observations appropriate for the purpose of analysis. For continuous parameters, descriptive statistics will include n (number of subjects or observations), mean, standard deviation, median, and range. Two-sided 95% CIs will be provided for all study outcomes.
 
The modified Intent-to-Treat (mITT) Population (defined as all subjects who were enrolled and received at least one application with the study device) will be used for analyses of safety and effectiveness endpoints. A Per-Protocol (PP) Population will neither be defined nor analyzed.

Clinical Trial Protocol ATM-2201	Version 2.0 28-Oct-2022	Confidential Page 6/25
-------------------------------------	----------------------------	---------------------------

SCHEDULE OF EVENTS AND PROCEDURES

Visit Number	V1	V2	V3	V4	V5	V6
Day/Week/Month	Day 1	24hr Post-Inj.	48hr Post-Inj.	72hr Post-Inj.	Day 7 ±1 day	Day 14 ±2 days
Assessment and Procedures						
Informed Consent	X					
Inc/Excl Criteria	X					
Demographics, Med Hx	X					
Concomitant Medications	X	X	X	X	X	X
Intralesional Injection(s)	X					
Investigator Assessments						
Global Severity Score	X					
Target Lesion Assessments	X	X	X	X	X	X
Target Lesion Photography	X pre-/post- inj.	X	X	X	X	X
Lesion Injection Videography	X					
Subject Assessments						
Target Lesion Pain	X pre-inj.	X	X	X	X	X
Intralesional Injection Pain	X post- inj.					
Subject Satisfaction		X	X	X	X	X
Safety Assessments						
UPT (as applicable)	X					
Adverse Events	X	X	X	X	X	X

Clinical Trial Protocol ATM-2201	Version 2.0 28-Oct-2022	Confidential Page 7/25
-------------------------------------	----------------------------	---------------------------

TABLE OF CONTENTS

PROTOCOL APPROVAL SIGNATURE PAGE	2
INVESTIGATOR SIGNATURE PAGE	3
SYNOPSIS	4
1 INTRODUCTION	9
2 STUDY OBJECTIVE	9
3 COMPLIANCE STATEMENT	9
3.1 Variations to the Protocol	9
3.2 Investigational Sites	9
4 OVERVIEW OF STUDY DESIGN	10
5 STUDY POPULATION	10
5.1 Inclusion Criteria	10
5.2 Exclusion Criteria	10
5.3 Subject Withdrawal	11
6 SUBJECT NUMBERING, RANDOMIZATION AND BLINDING.....	11
7 CONCOMITANT AND PROHIBITED MEDICATION/PROCEDURES	11
7.1 Concomitant Medications and Procedures	11
8 INVESTIGATIONAL PRODUCT MANAGEMENT	11
8.1 Intradermal Needle Adapter	11
8.2 Triamcinolone for Injection.....	12
9 STUDY EVALUATIONS	12
9.1 Visit Procedures.....	12
9.1.1 Visit 1 (Baseline; Day 1).....	12
9.1.2 Visits 2 to 6 (24hr , 48hr, 72hr, 7 days, 14 days).....	13
9.2 Investigator Assessments.....	13
9.2.1 Global Severity Score (GSS).....	13
9.2.2 Target Lesion Assessments	13
9.2.2.1 Target Lesion Erythema	13
9.2.2.2 Target Lesion Severity.....	14
9.2.2.3 Target Lesion Improvement	14
9.2.2.4 Target Lesion Videography	14
9.2.2.5 Target Lesion Photography.....	14
9.3 Subject Assessments.....	14
9.3.1 Target Lesion Pain	14
9.3.2 Intralesional Injection Pain	14
9.3.3 Subject Satisfaction	15
9.4 Safety	15
9.4.1 Adverse Events	15
9.4.1.1 Definition of Adverse Event.....	15
9.4.1.2 Documenting Adverse Experiences.....	15
9.4.1.3 Serious Adverse Events	16
9.4.1.4 Assessment of Severity	16
9.4.1.5 Assessment of Causality	16
9.4.1.6 Reporting of Serious Adverse Events	17
9.4.1.7 Pregnancy	17
10 STATISTICS	17
10.1 Sample Size Determination	18

1 INTRODUCTION

Intralesional injection of corticosteroids is standard of care therapy for stubborn acne lesions. They are typically dosed with triamcinolone acetonide at concentrations of 0.5 mg/mL to 2.5 mg/mL (i.e., 0.5% to 2.5%) in volumes of 0.05 mL to 0.15 mL.

This proof-of-concept study will investigate the safety of using an intradermal needle adapter for delivery of intralesional triamcinolone injections in patients with acne vulgaris. The intradermal needle adapter is an accessory that slips on the end of a standard 32G 0.5" needle and reduces the effective length of the needle to 1mm. The adapter (currently a prototype) is made of biocompatible 304 Stainless Steel and is being developed to allow patients to safely self-inject triamcinolone, rather than depending on injections performed by a physician.

As intralesional triamcinolone injections are standard-of-care, the purpose of this proof-of-concept study is to test the safety of the intradermal needle adapter, not the safety and efficacy of triamcinolone per-se.

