3.1 Variations to the Protocol

No changes from the final approved (signed) protocol will be initiated without the prior approval by the IRB except 1) when necessary to eliminate immediate hazards to the subjects or when the change involves only logistics or administration, or 2) minor administrative or typographical corrections. The sites' PIs and the Sponsor must sign any protocol amendments.

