3.2 Investigational Sites

One (1) U.S. investigational site will participate in this study. The site must obtain written approval from a 21 CFR 56 compliant IRB prior to recruitment and enrollment of any subject into the study. Any changes to the study procedures must be made with the mutual agreement of the PI and the Sponsor, documented in an amendment to the protocol, and approved by the reviewing IRB.

Clinical Trial Protocol ATM-2201	Version 2.0 28-Oct-2022	Confidential Page 10/25
-------------------------------------	----------------------------	----------------------------

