8.2 Triamcinolone for Injection

A commercial supply of triamcinolone 10% for injection will be provided to the site and diluted with Saline to the appropriate concentration. The site will store triamcinolone as per the conditions described in the package insert.

A standard 32G 0.5" needle will be fixed to a 1.0 mL luer syringe and the syringe will be loaded with an appropriate volume and concentration of triamcinolone. A total of 0.05 mL to 0.15 mL of triamcinolone 0.5% to 2.5% will be injected into each target lesion. The choice of volume and concentration for each individual lesion will be at the discretion of the Investigator as per his clinical judgement. The intradermal needle adapter will then be installed on the needle.

At least one (1), and up to three (3) inflammatory target lesions will be selected for intralesional injections of triamcinolone using the intradermal needle adapter.

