11 QUALITY CONTROL AND QUALITY ASSURANCE

11.1 Study Monitoring

An initiation webinar will be conducted with the PI and study coordinator(s) by Sponsor and/or its designee. During this meeting, an extensive review and discussion of the protocol, all study procedures, source documents, and CRFs will be conducted. Evaluation scales will be reviewed extensively.

The Clinical Project Manager(s) and Clinical Trial Associate(s) will be trained prior to study initiation.

The conduct of the study will be closely monitored by the Sponsor (or designate) following GCP guidelines. The reports of these verifications will also be archived with the study report. In addition, inspections or on-site audits may be carried out by local and/or federal authorities. The PIs will allow the Sponsor's representatives and any regulatory agency to examine all study records, corresponding subject medical records, clinical dispensing records and storage area, and any other documents considered source documentation. The PIs agree to assist the representative, if required.

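### Section 1 equates 0.5–2.5 mg/mL with 0.5%–2.5%, a tenfold mismatch by % w/v, while the injection instruction and the stock strength are given in percent only

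*Combined protocol and SAP*

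**What the plan says.** Section 1 (Introduction), as background on usual practice, gives triamcinolone acetonide at "concentrations of 0.5 mg/mL to 2.5 mg/mL (i.e., 0.5% to 2.5%) in volumes of 0.05 mL to 0.15 mL". This is the only place in the protocol where a concentration appears in mg/mL, and the only place where percent is tied to a mass.

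The instruction the site will follow is in the Synopsis (Study Treatment) and Section 8.2, in the same words: "A total of 0.05 mL to 0.15 mL of triamcinolone 0.5% to 2.5% will be injected into each target lesion". No mg/mL value accompanies it.

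Section 8.2 describes the stock as follows: "A commercial supply of triamcinolone 10% for injection will be provided to the site and diluted with Saline to the appropriate concentration". This too is in percent only. It then says: "The choice of volume and concentration for each individual lesion will be at the discretion of the Investigator as per his clinical judgement".

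Neither the Synopsis nor Section 8.2 refers back to Section 1 for the meaning of percent.

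**The concern.** For an injectable solution, percent is ordinarily read as weight per volume: grams per 100 mL. On that reading the equivalence in Section 1 is false by a factor of ten. The only other reading that makes it true is a shorthand in which 1% means 1 mg/mL, and the protocol never says it uses one.

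The slip would matter little if it stayed in the background text. It does not, because the same percentages and volumes become the injection instruction. The site dilutes the stock itself and the investigator chooses volume and concentration lesion by lesion. In the operative text the percent range is the only stated limit on concentration, and what it permits differs tenfold according to the convention. For the same reason, that text does not settle whether a given preparation is within protocol.

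**Working it through.** **Inputs.** Concentration: 0.5–2.5 mg/mL, equated with 0.5%–2.5% (Section 1). Volume per lesion: 0.05–0.15 mL (Section 1, Synopsis, Section 8.2). Stock: 10% (Section 8.2). Lesions per subject: one to three (Synopsis, Section 8.2). The vial's strength in mg/mL is not in the documents, so only the two values that 10% could imply are used.

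**The plan's own equivalence.** 1% w/v = 1 g/100 mL = 1000 mg/100 mL = 10 mg/mL. Hence:

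- 0.5% = 0.5 × 10 = 5 mg/mL and 2.5% = 2.5 × 10 = 25 mg/mL.
- Conversely, 0.5 mg/mL = 0.05% and 2.5 mg/mL = 0.25%.

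The stated equality is not reproduced. The ratio is 5/0.5 = 25/2.5 = 10 at both ends. The ranges do not overlap, since the top of one (2.5 mg/mL) is half the bottom of the other (5 mg/mL).

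**Each convention applied throughout.** Mass = concentration × volume; dilution factor = stock ÷ target.

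| | Section 1's equation (1% = 1 mg/mL) | % w/v (1% = 10 mg/mL) |
|---|---|---|
| Stock | 10 mg/mL | 100 mg/mL |
| Target | 0.5–2.5 mg/mL | 5–25 mg/mL |
| Dilution factor | 10/0.5 = 20 to 10/2.5 = 4 | 100/5 = 20 to 100/25 = 4 |
| Lowest mass per lesion | 0.05 × 0.5 = 0.025 mg | 0.05 × 5 = 0.25 mg |
| Highest mass per lesion | 0.15 × 2.5 = 0.375 mg | 0.15 × 25 = 3.75 mg |
| Highest mass, three lesions | 3 × 0.375 = 1.125 mg | 3 × 3.75 = 11.25 mg |

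The per-lesion masses overlap only from 0.25 to 0.375 mg. Each column is coherent in itself, and the dilution factors are the same in both.

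**Conventions mixed between stock and target.** Stock needed is shown per 1.0 mL prepared, which is a convenient basis and not a volume the protocol sets.

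- *10 mg/mL vial, w/v target.* At nominal 0.5%: 5/10 = 0.5 mL of stock. At nominal 1.0%: 10/10 = 1.0 mL, undiluted. At nominal 2.5%: 25/10 = 2.5 mL, which is impossible. From 0.5% to 1.0% the result is ten times the Section 1 reading; above 1.0% the target cannot be reached from this stock.
- *100 mg/mL vial, mg/mL target.* 0.5/100 = 0.005 mL to 2.5/100 = 0.025 mL of stock, a 200- to 40-fold dilution. The result is one tenth of the w/v reading across the whole range.

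**The case against.** The best defence is that Section 1 does supply a convention. It says outright that the mg/mL range and the percent range are the same thing, and the operative sections repeat the same percentages and volumes. Carried through, this gives a coherent reading: a 10 mg/mL stock diluted 4- to 20-fold. The treatment is described as standard of care and Section 1 states the usual concentration in mg/mL, which also points to one reading. Stock and target share one notation within Section 8.2, so a reader who treats them alike gets the same dilution under either convention. A tenfold preparation difference requires mixing conventions, and how likely that is depends on facts outside the documents.

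There are practical safeguards too. There is one site, and at initiation "an extensive review and discussion of the protocol, all study procedures, source documents, and CRFs will be conducted". The instruction that "The site will store triamcinolone as per the conditions described in the package insert" implies that the insert is at hand, though that sentence concerns storage only. Finally, the objective is the safety of the adapter, not of the drug.

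Much of this stands. A consistent reading exists, and the chance of a misreading may be low. But the one sentence linking percent to mass is background on typical practice, conflicts with ordinary % w/v, and is not stated to govern the Synopsis or Section 8.2. The safeguards may catch a misreading; they do not correct the text.

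**Conclusion.** The concern holds. The equivalence in Section 1 is wrong by exactly ten under % w/v, and the injection instruction and stock strength rest on percent figures whose convention is not declared. The instruction can be read as permitting 0.025–0.375 mg or 0.25–3.75 mg per lesion. The defect is a false equivalence and an undeclared governing unit, not the absence of any consistent reading.

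The consequence is conditional. With one convention used for both stock and target, the dilution does not change and the mass delivered follows the vial's true strength, which is unknown here. With conventions mixed, the preparation can differ by up to tenfold in either direction, subject to the stock-strength limit shown above. Nothing here implies which reading is intended.

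The sample size of about 20, which has no formal justification, and the descriptive analysis are untouched. The point must be fixed because it is an unresolved tenfold ambiguity in an instruction to inject a drug.

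**What to change.** The sponsor and investigator should reconcile Section 1, the Synopsis (Study Treatment) and Section 8.2. They should correct the equivalence in Section 1 and give both the target concentration and the stock strength in one explicit mass-per-volume unit wherever they appear. Deleting the parenthesis in Section 1 would not be enough: it would remove the only link between percent and mass and leave undefined percentages in the other two places. The intended concentration is theirs to settle, and no value is proposed here.

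The cost is a wording change in three places, with no extra subjects, visits, procedures or analyses. For IRB handling, Section 3.1 exempts "minor administrative or typographical corrections" from prior approval, whereas Section 3.2 requires changes to study procedures to be "documented in an amendment to the protocol, and approved by the reviewing IRB". Whether the exemption covers a correction to a stated drug concentration is arguable, so the route should be decided explicitly.

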2 STUDY OBJECTIVE

The objective of this proof-of-concept study is to investigate the safety of using an intradermal needle adapter for performing intralesional injections.

3 COMPLIANCE STATEMENT

The study will be conducted in accordance with the Clinical Investigation Plan, International Conference on Harmonization (ICH) and Good Clinical Practice (GCP), the Declaration of Helsinki, International Organization for Standardization (ISO) 14155, and the United States (US) Code of Federal Regulations (CFR) applicable to clinical studies (45 CFR Part 46, 21 CFR Part 50, 21 CFR Part 56, and 21 CFR Part 312). In addition, the study will be conducted in compliance with all applicable laws and regulatory requirements relevant to the use of new medical devices in the United States.

The sites' Principal Investigator (PI) is responsible for ensuring the privacy, safety and welfare of the subjects during and after the study and must ensure that site personnel are appropriately trained. The PI at each site has the overall responsibility for the conduct and administration of the study at their site, and for contact with study site management, and local authorities.

3.1 Variations to the Protocol

No changes from the final approved (signed) protocol will be initiated without the prior approval by the IRB except 1) when necessary to eliminate immediate hazards to the subjects or when the change involves only logistics or administration, or 2) minor administrative or typographical corrections. The sites' PIs and the Sponsor must sign any protocol amendments.

3.2 Investigational Sites

One (1) U.S. investigational site will participate in this study. The site must obtain written approval from a 21 CFR 56 compliant IRB prior to recruitment and enrollment of any subject into the study. Any changes to the study procedures must be made with the mutual agreement of the PI and the Sponsor, documented in an amendment to the protocol, and approved by the reviewing IRB.

Clinical Trial Protocol ATM-2201	Version 2.0 28-Oct-2022	Confidential Page 10/25
-------------------------------------	----------------------------	----------------------------

4 OVERVIEW OF STUDY DESIGN

This is an open-label, prospective, single-arm study. Approximately 20 subjects will be enrolled at 1 study site. A full description of the inclusion and exclusion criteria can be found in Section 5.

All subjects will receive standard-of-care intralesional injection with triamcinolone using an intradermal needle adapter at Visit 1 (Day 1). Subjects will then attend in-clinic visits at Visit 2 (24-hours post-injection), Visit 3 (48-hours post-injection), Visit 4 (72-hours post-injection), Visit 5 (Day 7), and Visit 6 (Day 14).

